11.1 Adverse Events

Adverse events will be coded using Version 18.0 or newer of the Medical Dictionary for Regulatory Activities.

An AE (classified by preferred term [PT]) that occurs during the Evaluation Period will be considered a TEAE if it has a start date on or after the first dose of investigational product or if it has a start date before the date of the first dose of investigational product, but increases in severity on or after the date of the first dose of investigational product. If more than 1 AE with the same PT is reported before the date of the first dose of investigational product, then the AE with the greatest severity will be used as the benchmark for comparison to the AEs occurring during the Evaluation Period under the preferred term. An AE that occurs more than 3 days after the date of the last dose of investigational product will not be counted as a TEAE.

An overall summary of number of subjects with TEAEs in each treatment group will be presented by treatment group, including the number and percentage of subjects with any TEAEs, serious TEAEs, TEAEs related to investigational product, TEAEs leading to withdrawal, severe TEAEs, and TEAEs leading to death.

Number and percentage of subjects reporting TEAEs in each treatment group will be tabulated by system organ class (SOC) and PT. TEAEs will be further summarized by maximum severity and relationship to investigational product. If more than 1 AE occurs with the same PT for the same subject, then the subject will be counted only once for that PT using the most severe and most related occurrence for the summarization by severity and by relationship to investigational product.

The incidence of TEAEs, serious TEAEs, and TEAEs leading to withdrawal will be summarized by SOC, PT, and treatment group, sorted in decreasing frequency for subjects on SPD489 then for placebo. The incidence of common ($\geq 2\%$ of subjects in any treatment group) will be summarized by PT and treatment group, sorted in decreasing frequency for subjects on SPD489 and then for placebo.

The number and percentage of subjects reporting TEAEs over the Safety Analysis Set will also be presented by week of AE onset, preferred term and treatment group, where week of AE onset is calculated as (AE occurred date – first dose date + 1) / 7, then rounded up to an integer.

All information about AEs collected on the electronic case report form will be listed alongside the dose, PT, and SOC. For serious TEAEs, deaths, AEs related to the investigational product, and TEAEs leading to study discontinuation, a separate listing will also be provided.

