#### **8.1.1 Severity Categorization**

The severity of AEs must be recorded during the course of the event including the start and stop dates for each change in severity. An event that changes in severity should be captured as a new event. Worsening of pre-treatment events, after initiation of investigational product, must be recorded as new AEs (for example, if a subject experiences mild intermittent dyspepsia prior to dosing of investigational product, but the dyspepsia becomes severe and more frequent after first dose of investigational product has been administered, a new AE of severe dyspepsia [with the appropriate date of onset] is recorded on the appropriate CRF).

The medical assessment of severity is determined by using the following definitions:

**Mild:** A type of AE that is usually transient and may require only minimal treatment or therapeutic intervention. The event does not generally interfere with usual activities of daily living.

**Moderate:** A type of AE that is usually alleviated with specific therapeutic intervention. The event interferes with usual activities of daily living, causing discomfort but poses no significant or permanent risk of harm to the research subject.

**Severe:** A type of AE that interrupts usual activities of daily living, or significantly affects clinical status, or may require intensive therapeutic intervention.

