## 9.9 Safety Analyses

The Safety Analysis Set based on either the interim analysis dataset or all cumulative data up to study completion, whenever it is appropriate, will be used to report the safety data.

Clinical laboratory tests, vital signs, and ECG findings will be summarized by treatment group and visit using appropriate descriptive statistics. Potentially clinically important findings will also be summarized by treatment group and listed.

Adverse events will be coded using the Medical Dictionary for Regulatory Activities. TEAEs are defined as AEs that start or deteriorate on or after the date of the first dose of investigational product and no later than 3 days following the last dose of investigational product in the double-blind phase.

Treatment-emergent AEs will be summarized. The number and percent of subjects with TEAEs will be calculated for each system organ class, by preferred term, and by treatment. The severity of the TEAEs, the relationship to the investigational product, TEAEs causing study discontinuation, serious AEs and death will also be presented.

The CSHQ will be summarized by treatment group using appropriate descriptive statistics at each visit.

Sleep diary data will be descriptively summarized by treatment group.

A summary and listing of the C-SSRS data will be provided for subjects with a positive response only.

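### Each severity change becomes a new AE record, but SAP 11.1 has no rule for joining records of one episode, so onset weeks multiply and the TEAE rule is unclear for pre-dose events that improve

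*SAP*

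**What the plan says.** **Recording.** Protocol 8.1.1 asks for severity over the course of an event, "including the start and stop dates for each change in severity". It then says: "An event that changes in severity should be captured as a new event". That sentence has no direction; it covers easing as well as worsening. Worsening of events present before treatment is dealt with separately in the next sentence: "Worsening of pre-treatment events, after initiation of investigational product, must be recorded as new AEs".

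**Protocol definition of a TEAE.** Protocol 9.9 (and the Synopsis) states that "TEAEs are defined as AEs that start or deteriorate on or after the date of the first dose of investigational product", with a cut-off 3 days after the last dose.

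**SAP definition of a TEAE.** SAP 11.1 has two limbs joined by *or*. Under limb 1, an AE in the Evaluation Period "will be considered a TEAE if it has a start date on or after the first dose of investigational product". Under limb 2, an AE that began before the first dose also qualifies if it did so "but increases in severity on or after the date of the first dose of investigational product". A benchmark sentence follows: if more than one AE with the same preferred term was reported before the first dose, "then the AE with the greatest severity will be used as the benchmark for comparison to the AEs occurring during the Evaluation Period". The same 3-day cut-off applies. SAP 17 declares no change from the protocol's analyses.

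**Counting.** SAP 11.1 counts a subject once per preferred term, and ties that rule to the summaries by severity and by relationship. In a later paragraph, the numbers of subjects with TEAEs "will also be presented by week of AE onset, preferred term and treatment group". The week is the AE date minus the first-dose date plus 1, divided by 7 and rounded up.

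**The concern.** The recording rule splits one clinical episode into several dated records, and the analysis rules take dated events as their input. Nothing in either document joins the pieces again. Two things follow.

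First, the onset-week table can report a change in severity as if it were a new event. Children start at 5 mg and are titrated over the first three weeks (Protocol 6.2.3 and 7.1.2.1), so a reader will use this table to see when events begin during titration. A mild event that becomes moderate in Week 2 would look like a fresh Week 2 onset.

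Second, a symptom noted in screening or washout that eases after the first dose acquires a record with a post-dose start date. Limb 1 has no severity condition and no link back to the pre-dose record, so on its face it counts that improvement as treatment-emergent, although the protocol's definition covers only events that start or deteriorate. AEs are collected from consent and asked about at the washout call (Protocol 8.1 and 7.1.1.2), so such records are possible. Two programmers could reach different TEAE counts from the same data.

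**Working it through.** The plan states no figure on this point, so there is none to reproduce. The check applies the written rules to assumed records.

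**Inputs from the documents**
- A new dated record at each severity change (Protocol 8.1.1).
- TEAE limb 1: start on or after first dose, no severity condition (SAP 11.1).
- Onset week = ceil((AE date − first-dose date + 1)/7) (SAP 11.1).
- 195 randomised in a 5:5:5:5:6 ratio, which sums to 26 (Protocol 9.6).

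**Assumed for illustration:** the event dates and severities. Day = AE date − first-dose date + 1, so the day of first dose is day 1.

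| Case | Records | Limb 1 read literally, record by record | Linked episode, worse than pre-dose required |
|---|---|---|---|
| A: pre-dose event improves | moderate day −4; mild day 3 | 1 TEAE, week ceil(3/7) = 1 | no TEAE |
| B: pre-dose event worsens | mild day −4; moderate day 3 | 1 TEAE, week 1 | 1 TEAE, week 1 |
| C: one on-treatment episode | mild day 3; moderate day 10; mild day 18 | weeks ceil(3/7) = 1, ceil(10/7) = 2, ceil(18/7) = 3 | week 1 only |

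**Does the benchmark sentence settle these cases?** In case C there is no pre-dose event, so it has no effect. In case A there is one pre-dose AE of the preferred term, and the sentence is conditioned on more than one. Even where it applies, it names a comparator without saying that a post-dose event no worse than that comparator is left out.

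**Which tables are affected?** Tables by system organ class and preferred term count subjects, so the repeat records in case C leave them unchanged; only case A can raise them. The onset-week table is exposed to both.

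**Size of one child.** Active arm: 195 × 5/26 = 37.5, and 1/37.5 = 2.7 percentage points. Placebo: 195 × 6/26 = 45, and 1/45 = 2.2 points. The documents give no AE frequencies and no rates of severity change, so the number of such children cannot be computed.

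**The case against.** The best defence concerns case A. SAP 11.1 frames an AE by preferred term, not by case report form record. If every severity change is a new record, no single record can start before the first dose and then worsen, so a record-level reading leaves limb 2 empty and the benchmark with nothing to do. Read by preferred term, both work: pre-dose severity is compared with post-dose severity, and an event that only improves is not a TEAE. SAP 18.9 points the same way, since imputing a mild grade for a missing pre-dose severity makes sense mainly if that severity serves as a comparator. This stands as evidence of intent. It does not remove the conflict, because limb 1 carries no severity condition and the benchmark states no exclusion.

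On case C, the defence is that the table counts subjects, that a once-per-term rule exists, and that table specifications sit in a separate document (SAP 1) which may settle the counting. But the once-per-term rule is written for other summaries, and nothing in the two documents reviewed extends it to this table.

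It is also fair that any error in case A overstates harm, which is the cautious direction, and that no inferential result depends on it. Finally, linking by contiguous dates needs stop dates, and SAP 18.8 by default imputes only start dates; the fix therefore has to say what happens when a stop date is missing.

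**Conclusion.** The concern holds in a limited form. The onset-week effect follows from the text as written, and no other section corrects it. For improving pre-dose events the SAP conflicts with itself and, read literally, with the protocol; it is an ambiguity to be resolved, not an established misclassification. The consequence is confined to descriptive safety tables, and the number of children involved is unknown.

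Four stronger readings are tempting but not supported:
- A reader might infer that TEAE incidence is inflated throughout. Subject-level counts can rise only through improving pre-dose events, and only if limb 1 is applied literally.
- A reader might infer that the inflation is greater in arms where symptoms ease. The documents contain no data on this.
- A reader might infer that the onset-week table is the sole view of events against dose. SAP 11.1 also lists AEs alongside the dose, so a severity change can be traced there; the table is only the sole planned summary by time of onset. Nor does a later week always mean a higher dose: placebo and 5 mg have no dose steps, and dose is fixed after titration.
- A reader might treat passing the SAP's 2% threshold for common events as a measure of the problem. In arms of 37.5 and 45, any single event in any child passes it.

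The conclusion assumes that sites follow Protocol 8.1.1 as written and that no unseen table specification already links the records.

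**What to change.** Add to SAP 11.1, before any unblinding, including that for the interim analysis, so that the choice between readings is not informed by the data:

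1. **Linking.** Records with the same preferred term and contiguous dates in one child form one episode. A record with a missing stop date is treated as continuing to the next record of that term.
2. **TEAE status.** An episode that began before the first dose is a TEAE only if its post-dose severity exceeds its worst pre-dose severity. A separate episode that starts after the first dose, once the pre-dose event has resolved, is a TEAE. This keeps a true recurrence at equal severity, which a benchmark applied to every same-term event would drop. The 3-day cut-off is unchanged.
3. **Onset week.** One per episode, from its first treatment-emergent record; for a worsened pre-dose event, the date of worsening. Maximum severity is tabulated as already planned.

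The cost is some SAP wording and a small derivation from dates and severities already collected. TEAE counts may fall slightly compared with a literal reading of limb 1. The missing-stop-date convention may occasionally merge two separate episodes, so the listings should keep every record as entered.

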### 7.1.4 Additional Care of Subjects After the Study

Subjects who have completed the study at Visit 6 end of study (EOS)/ET may be evaluated for eligibility to enter a long-term safety study of SPD489.

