## **8 ADVERSE AND SERIOUS ADVERSE EVENTS ASSESSMENT**

### **8.1 Definition of Adverse Events, Period of Observation, Recording of Adverse Events**

An AE is any untoward medical occurrence in a clinical investigation subject administered a pharmaceutical product and that does not necessarily have a causal relationship with this treatment. An AE can therefore be any unfavorable and unintended sign (including an abnormal laboratory finding), symptom, or disease temporally associated with the use of a medicinal (investigational) product, whether or not related to the medicinal (investigational) product (ICH Guidance E2A 1995).

All AEs are collected from the time the informed consent is signed until the defined follow-up period stated in Section 7.1.3. This includes events occurring during the screening phase of the study, regardless of whether or not investigational product is administered. Where possible, a diagnosis rather than a list of symptoms should be recorded. If a diagnosis has not been made, then each symptom should be listed individually. All AEs should be captured on the appropriate AE pages in the CRF and in source documents. In addition to untoward AEs, unexpected benefits outside the investigational product indication should also be captured on the AE CRF.

All AEs must be followed to closure (the subject's health has returned to his/her baseline status or all variables have returned to normal), regardless of whether the subject is still participating in the study. Closure indicates that an outcome is reached, stabilization achieved (the investigator does not expect any further improvement or worsening of the event), or the event is otherwise explained. When appropriate, medical tests and examinations are performed so that resolution of event(s) can be documented.

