## 9.5 Planned Interim Analysis, Adaptive Design, and Data Monitoring Committee

### 9.5.1 Interim Analysis

The study implements a group sequential design with one interim analysis. The interim analysis is proposed when approximately 60% of planned subjects who either complete or discontinue the study.

The interim analysis will be conducted on the interim analysis dataset, which is defined as all data from 60% of initially planned subjects who have either completed or discontinued the study, together with data for subjects who are in the study up to the interim analysis data cut time point. The efficacy, safety, and sensitivity on missing data mechanisms analyses at the interim analysis will primarily be conducted using this dataset.

The Lan-DeMets alpha spending function with O'Brien-Fleming boundary will be used for alpha spending between the interim and EOS analysis for the primary efficacy endpoint. Following evaluations in the stage-wise hierarchical setting ([Glimm et al. 2010](#)), the Lan-DeMets alpha spending function with Pocock boundary will be applied to analyze the key secondary efficacy endpoint. This approach will strongly control the study-wide type I error at the overall 0.05 significance level, and in general increase power for the test on the key secondary endpoint.

If the hypothesis for the primary efficacy endpoint is rejected at the interim analysis, then the study will be stopped for efficacy and all ongoing subjects from the study (SPD489-347) will be immediately rolled over to the open-label extension study (Study SPD489-348). In this case, using the same data cut point that contains the same information fractions as the primary efficacy interim analysis, the key secondary efficacy endpoint will be tested. In addition, the incremental data collected during the interim analysis process, i.e., the overrun, together with the interim analysis dataset will be utilized in sensitivity analyses for major efficacy and safety end points. Otherwise, if the primary efficacy criterion is not met at the interim analysis, then the hypothesis for the key secondary endpoint will not be tested at this time, and the study will continue to its completion, then the primary efficacy endpoint will be tested.

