2. STUDY DESIGN

2.1 General Study Design

This is a Phase 3, randomized, double-blind, multicenter, parallel-group, placebo-controlled, fixed-dose study to evaluate the safety and efficacy of SPD489 compared to placebo, administered as a daily morning dose in the treatment of preschool children 4-5 years of age, diagnosed with attention deficit/hyperactivity disorder (ADHD).

[figure not shown]
A randomized design is used to avoid baseline characteristics selection bias for different treatment groups on the part of the participants and investigators. Blinded treatment is used to reduce potential bias during data collection and evaluation of clinical results. The placebo arm is used to control the subject's expectation that a treatment would have an effect, to optimize sensitivity, to maintain the scientific rigor of the study, and to validate the study internally.

The study has 4 periods: 1) Screening and Washout; 2) Fixed-dose titration; 3) Dose Maintenance; and 4) Safety Follow-up. The duration of the double-blind evaluation period (Fixed-dose titration and Dose-maintenance Periods) will be 6 weeks.

The study will be conducted in up to 60 sites in the North America. The subject's maximum duration of participation is expected to be approximately 11 weeks. The study will be completed in approximately 24 months. Subjects will be randomized at baseline (Visit 0) in a 5:5:5:6 ratio to SPD489 5, 10, 20, 30mg or placebo group. Approximately 25% of the subjects enrolled will be female. Subjects are titrated to the randomly assigned dose strength of the investigational product (refer to SPD489-347 Protocol, Section [6.2.3](#)).

SPD489 will be provided in dose strengths of 5, 10, 20 and 30 mg, and matching placebo will also be provided. Visits and phases are presented graphically in [Figure 1](#).

Figure 1: Study Design Flow Chart

ET = early termination, V = visit, W = week, WO = washout.

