2.6.2 Interim Analysis

The Lan-DeMets alpha spending function with O'Brien-Fleming boundary will be used for alpha spending between the interim and end of study analysis for the primary efficacy endpoint. Following evaluations in the stage-wise hierarchical setting ([Glimm et al. 2010](#)), the Lan-DeMets alpha spending function with Pocock boundary will be applied to analyze the key secondary efficacy endpoint.

If the hypothesis for the primary efficacy endpoint is rejected at the interim analysis, then the study will be stopped for efficacy and all ongoing subjects from the study (SPD489-347) will be immediately rolled over to the open-label extension study (Study SPD489-348). In this case, using the same data cut point that contains the same information fractions as the primary efficacy interim analysis, the key secondary efficacy endpoint will be tested, and all safety summaries that the DMC to be needed for their decision will be generated, which will include disposition, demographic and baseline characteristics, main AE and vital signs information. Additionally, the incremental data collected during the interim analysis process, i.e., the overrun, together with the interim analysis dataset will be utilized in sensitivity analyses for efficacy and safety. Otherwise, if the primary efficacy criterion is not met at the interim analysis, then the hypothesis for the key secondary endpoint will not be tested at this time, and the study will continue to its completion, at which time the primary efficacy endpoint will be tested. If the primary efficacy test is rejected, then the key secondary efficacy endpoint will be tested. This testing procedure strongly protects the overall alpha level for the primary and key secondary efficacy analyses. All other efficacy and safety analyses will be conducted at this time as well.

At the interim or final efficacy analysis, only the primary efficacy result will be used to determine if the study meets the efficacy criterion. The nominal significance level for the interim or final primary and key secondary efficacy endpoints for a 2-sided at a 0.05 significant level are specified below, calculated using East® 6.4. The calculations are based on 60% of

planned sample size at the interim analysis, and the significance values may be updated (in a blinded fashion), based on the actual information fraction at the interim analysis.

[figure not shown]
| | Efficacy Boundary p-value Scale | |

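### The TEAE window has no cut at the first open-label SPD489 dose, so after an interim efficacy stop open-label events can be tabulated under the randomised arm, including placebo

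*SAP*

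**What the plan says.** Protocol 9.9, like the synopsis, counts adverse events that begin or worsen from the first dose to "no later than 3 days following the last dose of investigational product in the double-blind phase". SAP 11.1 sets the same outer limit without naming the double-blind phase: "An AE that occurs more than 3 days after the date of the last dose of investigational product will not be counted as a TEAE". It also carries a second condition: "An AE (classified by preferred term [PT]) that occurs during the Evaluation Period will be considered a TEAE". SAP 2.1 gives that period a length: "The duration of the double-blind evaluation period (Fixed-dose titration and Dose-maintenance Periods) will be 6 weeks".

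Two routes lead from this study to open-label SPD489.

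- **Interim efficacy stop.** Protocol 9.5.1 says that all ongoing children "will be immediately rolled over to the open-label extension study" (SPD489-348), and SAP 2.6.2 repeats this. SAP 11 then bases safety reporting on the interim dataset plus the overrun.
- **Visit 6 or early termination.** Protocol 7.1.4 says only that these children "may be evaluated for eligibility to enter a long-term safety study of SPD489". It gives no start date for dosing.

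Collection of events in this study outlasts the last dose: "All AEs are collected from the time the informed consent is signed until the defined follow-up period stated in Section 7.1.3". Section 7.1.3 sets that follow-up at 7 (+3) days and makes no exception for children who roll over. SAP 11 reports safety by dose strength, pooled doses and placebo. The data handling rules in SAP 18 do not mention open-label dosing, and SAP 17 declares no change from the protocol.

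**The concern.** A 3-day tail is meant to catch late effects of the randomised treatment. It does that only while the child takes nothing else that could cause the event. A placebo child who starts SPD489 within the tail can have an event caused by active drug, and the rule would still count it as a placebo TEAE. A child from a 5, 10, 20 or 30 mg arm could likewise have an event on the extension's dose counted under the randomised dose.

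Safety and tolerability is a stated secondary objective (Protocol 2.2.2). Protocol 1.2.2 lists decreased appetite and insomnia among the most frequent events with this drug. Events of that kind in the placebo column would narrow the contrast the safety tables are there to show. The concomitant medication tables would not reveal the exposure, because SAP 9 does not count a medication started after the last dose of investigational product as concomitant.

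**Working it through.** **Arm sizes (Protocol 9.6).** The plan's own figures come first: 156 completers / (1 − 0.20) = 195 randomised, as stated. Placebo share of 5:5:5:5:6 is 6/26, so 195 × 6/26 = 45 placebo children, and 45 × 0.8 = 36 completers, as stated.

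**Days of overlap.** Let *gap* be the number of days from the last double-blind dose to the first open-label dose. The window includes day 3 after the last dose, so overlap = max(0, 3 − gap + 1). The earliest start considered is the next day.

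| Gap (days) | Window days on open-label drug |
|---|---|
| 1 | 3 |
| 2 | 2 |
| 3 | 1 |
| 4 or more | 0 |

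The documents do not give the gap. Immediate rollover after an interim stop points to a short one; for Visit 6 or early termination nothing is stated.

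**Children exposed on the interim-stop route.** The interim takes place when about 60% of planned children have completed or discontinued. That leaves at most 0.40 × 195 = 78 children, of whom 78 × 6/26 = 18 are on placebo (equally 0.40 × 45). This is a ceiling: some will not yet be enrolled, and some will finish during the analysis, which may take up to 8 weeks. The interim is waived altogether if nearly all remaining children would be enrolled in that time.

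**Weight of one child.** 1/45 = 2.2% of the full placebo arm.

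**Scale only, on an assumed rate.** Suppose 2%, 5% or 10% of the 18 had a new event on open-label drug within the window. These rates are not in the documents. The extra placebo children would be 18 × 0.02 = 0.36, 18 × 0.05 = 0.9 or 18 × 0.10 = 1.8, which is 0.8, 2.0 or 4.0 percentage points of 45. For the any-TEAE row this is too high, because a child with an earlier TEAE is already counted.

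**Does the Evaluation Period condition close the gap?** Take a child whose last double-blind dose is on day 20 and who starts open-label drug on day 21. There are three readings.

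1. *Six weeks from first dose.* Days 21 to 23 lie inside the period, so open-label events count. Only children who complete all six weeks are protected.
2. *The child's own double-blind dosing.* All post-dose events drop out. The SAP's 3-day sentence then does nothing for anyone and contradicts Protocol 9.9.
3. *Double-blind dosing plus 3 days.* This agrees with the protocol and leaves the gap open.

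Only the second reading closes the gap on the interim-stop route, and it is the one that conflicts with the protocol.

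**The case against.** The strongest reply is that SAP 11.1 already confines TEAEs to the Evaluation Period, so the 3-day sentence is only an outer exclusion. It would have work to do for children who stop dosing early. For children who complete six weeks, a literal reading does support this. It does not settle the matter for children moved over mid-period, and it departs from Protocol 9.9. It is an inconsistency to resolve and not a safeguard to rely on.

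The second reply is that the timing of extension dosing, and which study records events from then on, belong to the SPD489-348 protocol, which is not among these documents. That stands for the Visit 6 and early termination route. A reader might infer that all 36 placebo completers start open-label drug the day after Visit 6 and that placebo incidence rises by several percentage points. The documents do not support this: Protocol 7.1.4 speaks only of evaluation for eligibility, and a start on day 4 or later gives no overlap.

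Three further limits also stand.

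- It is tempting to say that one misplaced event lifts a preferred term over the SAP's 2% threshold for common TEAEs. At these arm sizes a single event does so in any arm (1/45 = 2.2% on placebo; 1/37.5 = 2.7% in an active arm), so this shows only that one event is visible.
- A reader might also infer that the bias always favours the drug. That is firm only for the placebo column. Active arms gain events too, and the direction there depends on extension dosing.
- TEAEs are also tabulated by week of onset and listed alongside dose. After a full 42 days of dosing, days 43 to 45 fall in week 7 and can be seen. For the child in the example, days 21 to 23 fall in weeks 3 and 4 and cannot be told apart. The SAP does not say whether the listed dose would be the open-label one.

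**Conclusion.** The point holds as a defect in the TEAE definition. Followed as written, Protocol 9.9 can place open-label events under the randomised arm, including placebo, and SAP 11.1 does not clearly prevent it. The interim-stop route is the one the documents support. The route after Visit 6 or early termination is conditional on a start date they do not give.

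The size cannot be derived from the documents. What can be said is that overlap is at most 3 days per child (assuming open-label dosing starts no earlier than the next day), that at most about 18 planned placebo children are exposed on the interim-stop route, and that each affected child moves the full-arm placebo incidence by up to 2.2 percentage points. The effect would raise placebo incidence; its direction in the active arms is uncertain. The safety tables are descriptive, and the primary and key secondary analyses, alpha and power are untouched. This is worth correcting before unblinding, so that attribution is not decided with results in view.

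**What to change.** In Protocol 9.9 (and the matching synopsis text) and SAP 11.1, end the TEAE window at the earlier of (a) 3 days after the last double-blind dose and (b) the day before the first open-label dose in SPD489-348. Apply this to events that worsen as well as to events that begin.

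In SAP 11.1, add that the last dose means the last dose in the double-blind phase, and define Evaluation Period to match this window. State that events starting on or after the first open-label dose are attributed to SPD489-348, and list them separately in this study's report.

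The cost is wording in two documents and one date brought in from the extension. The post-treatment window becomes slightly shorter for children who roll over. Collection of events under Protocol 8.1 need not change, so no safety information is lost.
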